#### - Definitions -

**The Peanut Protein ED** is the individual dose of peanut protein administered to subjects during the food challenge procedure, which triggers objective allergic reactions, leading to stopping the challenge. It is capped to 300 mg for the screening food challenge and 2,000 mg for the post-treatment food challenge at 12 months, with the starting dose of 1 mg. The ED is taken from the eCRF.

In the following two cases, the ED at the Month 12 DBPCFC is not documented in the eCRF by the investigator:

- if the Month 12 DBPCFC is stopped without symptoms leading to ending the DBPCFC (stopping rules). This situation is defined as intercurrent events in Table 3.
- if the subject took the 2,000 mg dose without any objective symptom leading to ending the DBPCFC. In this case, the last dose given at Month 12 DBPCFC will be considered for ED value.

#### Case of Partially ingested dose:

If the last dose given is only partially ingested by the subject prior to the DBPCFC stop, then the ED reported by the investigator is:

- the previous dose given if the quantity of the last dose given actually ingested by the subject is  $\leq$  to the previous dose ingested;
- the last dose given if the quantity of the last dose given actually ingested by the subject is  $>$  than the previous dose ingested.

Examples: If the last dose given is 1,000mg but only 200mg is actually ingested, then the recorded ED is 300mg. If the last dose given is 1,000mg and 400mg is actually ingested, then the recorded ED is 1000mg.

**The Peanut Protein CRD** is defined as the sum of all peanut protein doses taken by the subject during the DBPCFC (including the ED and any partial dose given before the reaction).

The CRD will be calculated as follow:

- If the ED reported by the investigator in the eCRF is missing, then the CRD is missing
- If the ED reported by the investigator in the eCRF is not missing then the CRD is calculated as the sum of all doses given, including also the partial doses; Example: If the set of recorded

	Statistical Analysis Plan	
	EPITOPE (V712-304) – Statistical Analysis Plan	
	Référence du Document /Document Reference : CCI	Page : 20 / 74

CCI

doses is {1, 3, 10, 30, 100, 90 (out of 300)}, and recorded ED = 100mg, then  $CRD = 1 + 3 + 10 + 30 + 100 + 90 = 234\text{mg}$ .

Note that ED and CRD will be recorded both for the placebo and the peanut day of the DBPCFC. Only the peanut day of DBPCFC and corresponding ED and CRD will be considered for the analyses.

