### 8.5.4 Other Efficacy Analyses

The percentage of subjects reaching a cumulative dose  $\geq 1,444$  mg peanut protein at Month 12, the percentage of subjects reaching a cumulative dose  $\geq 3,444$  mg peanut protein at Month 12, and the percentage of subjects unresponsive (i.e, showing no symptoms leading to stop the DBPCFC) to the highest dose (2,000 mg peanut protein) at Month 12 will be summarized descriptively by treatment group for the ITT population using missing=failure imputation method, as well as for the PP population.

No further adjustments will be made for the other efficacy endpoints for which p-values will be provided for descriptive purpose only. The following efficacy analyses will be performed using observed data (no imputation will be done).

- Peanut-specific IgE and IgG4 analysis over time: peanut-specific IgE and IgG4 levels at baseline and changes from baseline to Months 3, 6 and 12 will be summarized descriptively by treatment group on the ITT population, using observed data.

The mean change from Baseline of the peanut-specific IgE and IgG4 will be compared.

- Skin Prick Test analysis: The mean change from baseline at Months 3, 6 and 12 in mean wheal diameter will be evaluated for each treatment group on the ITT population using observed data.
- A quality of life score from the FAQLQ/FAIM Parent Form will be summarized at Month 12 and compared to baseline for both treatment groups for the overall ITT population, using observed data. FAQLQ-Parental Form (FAQLQ-PF) questionnaires will also be summarized by main domains of quality of life using specific scores:
  - Emotional impact,
  - Food-related anxiety,
  - Social and Dietary limitations.

The relationship between FAQLQ-PF scores and treatment response will also be studied.

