### Secondary analyses

Analyses of ED and CRD as continuous endpoints will be based on the FAS using:

- multiple imputation for subjects who were unable to perform the DBPCFC (intercurrent events 2 and 5, see section 5.4). For those subjects, the probability distribution that imputes the missing ED/CRD will rely on placebo subjects with an available response and so the missing data would mimic placebo response. Imputations will be performed using SAS® MI procedure generating 100 sets of imputed data. Seed used for imputation will be specified (details on the implementation of multiple imputations are given in Appendix 8.2)
- mBOCF method to impute missing data at Month 12 for subjects with intercurrent events 1 and 3 (see section 5.4):
  - mBOCF for ED is defined as follow:
    - If the DBPCFC is stopped without symptoms leading to ending the DBPCFC (stopping rules) or if the subject took the 2,000mg dose without any objective symptom leading to ending the DBPCFC, the ED value at Month 12 is considered as the maximum between:
      - the last dose given at Month 12 DBPCFC (if the last dose given at Month 12 DBPCFC is only partially ingested by the subject, then the rules as defined under partially ingested dose in section 5.4.1 will apply) AND
      - the ED value at screening
    - For the subjects who did not undergo the Month 12 DBPCFC, ED value at screening is carried forward at Month 12 using BOCF method.
  - mBOCF for CRD is defined as follows:
    - If the DBPCFC is stopped without symptoms leading to ending the DBPCFC (stopping rules) or if the subject took the 2,000mg dose without any objective symptom leading to ending the DBPCFC, the CRD value at Month 12 is considered as the maximum between:
      - the sum of all doses given at Month 12, including also the partial doses AND

CONFIDENTIEL / Ne pas diffuser sans autorisation de DBV

CONFIDENTIAL / Do not distribute without DBV authorization

	Statistical Analysis Plan	
	EPITOPÉ (V712-304) – Statistical Analysis Plan	
	Référence du Document /Document Reference : CCI	Page : 22 / 74

CCI

- the CRD value at screening
  - For the subjects who did not undergo the Month 12 DBPCFC, CRD at screening is carried forward at Month 12 using BOCF method.

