### 5.4.3 Other Efficacy Analysis/es

In this section the statistical analyses for the defined other efficacy endpoints will be described. For all endpoints, descriptive statistics and inferential analyses will be performed. All statistical measures (p-values and CIs) will only be of descriptive nature with no aim to draw confirmatory conclusions. If not stated otherwise, all analyses will be performed on the FAS.

No imputation for missing data is used for Other Efficacy variables, i.e. only observed data are presented, except for laboratory results reported as below the lower detection limit (or reported above a specific value) which will be imputed as described in section 5.1.

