#### 5.4.3.1 Treatment response based on Responder definitions

Based on the ED from the DBPCFC at Month 12 visit, using imputation method rules used for primary analysis (depending on intercurrent event type), the following will be defined:

- Subjects defined as treatment responders:
  - If the screening ED was  $\leq 10$  mg peanut protein and the ED is  $\geq 1,000$  mg peanut protein at the post-treatment DBPCFC at Month 12
  - OR
  - If the screening ED was  $> 10$  mg peanut protein and the ED is  $\geq 2,000$  mg peanut protein at the post-treatment DBPCFC at Month 12
- Subjects defined as treatment responders:
  - If the ED is  $\geq 1,000$  mg peanut protein at the post-treatment DBPCFC at Month 12, regardless the screening ED

Based on the CRD from the DBPCFC at Month 12 visit, using imputation method rules used for primary analysis (depending on intercurrent event type), the following will be defined:

CONFIDENTIEL / Ne pas diffuser sans autorisation de DBV

CONFIDENTIAL / Do not distribute without DBV authorization

	Statistical Analysis Plan	
	EPITOPE (V712-304) – Statistical Analysis Plan	
	Référence du Document /Document Reference : CCI	Page : 45 / 74

CCI

- The percentage of subjects reaching a CRD  $\geq 1,444$  mg peanut protein at Month 12 post-treatment DBPCFC
- The percentage of subjects reaching a CRD  $\geq 3,444$  mg peanut protein at Month 12 post-treatment DBPCFC
- The percentage of subjects who passed the Month 12 post-treatment DBPCFC (no stopping criteria leading to stopping the DBPCFC at 2,000 mg)

The number and percentage of subjects will be presented by treatment group.

The analysis will be performed on the FAS and PP set. Data from these endpoints will be included in a listing.

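### SAP 5.2.1 as written makes the Month 12 CRD missing for children who pass the whole challenge, and no sentence clearly restores it for the CRD ≥1,444 mg and ≥3,444 mg endpoints

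*SAP*

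**What the plan says.** SAP 5.2.1 names two situations in which the investigator enters no Month 12 ED in the eCRF. One is a challenge stopped without stopping symptoms. The other is a pass: "if the subject took the 2,000 mg dose without any objective symptom leading to ending the DBPCFC". For a pass, the section supplies an ED: "In this case, the last dose given at Month 12 DBPCFC will be considered for ED value".

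For CRD, the same section defines the quantity as the total of the peanut doses the child took, and then adds a calculation rule: "If the ED reported by the investigator in the eCRF is missing, then the CRD is missing".

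SAP 5.2.4, under Secondary analyses, introduces the "mBOCF method to impute missing data at Month 12 for subjects with intercurrent events 1 and 3". A sub-bullet there also covers the child who took 2,000 mg without "any objective symptom leading to ending the DBPCFC, the CRD value at Month 12 is considered as the maximum between" the sum of the Month 12 doses and the screening CRD.

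The CRD ≥1,444 mg and ≥3,444 mg endpoints are other efficacy endpoints. Three texts bear on them:
- SAP 5.4.3: "No imputation for missing data is used for Other Efficacy variables, i.e. only observed data are presented", with an exception only for laboratory values beyond a detection limit. The end of SAP 5.2.4 says the same in substance.
- SAP 5.4.3.1: "Based on the CRD from the DBPCFC at Month 12 visit, using imputation method rules used for primary analysis (depending on intercurrent event type".
- Protocol 8.5.4: these percentages "will be summarized descriptively by treatment group for the ITT population using missing=failure imputation method", and also for the per-protocol population.

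**The concern.** The repair that 5.2.1 makes for ED does not carry over to CRD, because the CRD rule depends on the ED that the investigator reported, not on the ED that the SAP derives. The children affected are those who tolerated every dose.

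If a programmer followed the 5.2.1 rule alone for the two threshold endpoints, only children who reacted after the full 2,000 mg dose could count as reaching 3,444 mg. Passers would leave the analysis. Alternatively, they would count as not reaching the threshold, since SAP 5.1 takes all subjects in the treatment group as the denominator. SAP 5.4.3.1 reports the percentage who passed beside the percentage reaching 3,444 mg. A child who ingested every dose in full belongs in both, so the second figure should not be the smaller. If passing is more common on active treatment, the literal rule would also understate the treatment difference.

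**Working it through.** **1. The plan's own figures.** The Month 12 dose steps in protocol 6.1.1.2 are 1, 3, 10, 30, 100, 300, 1,000 and 2,000 mg.
- 1 + 3 + 10 + 30 + 100 + 300 + 1,000 = 1,444 mg.
- 1,444 + 2,000 = 3,444 mg.
- The SAP 5.2.1 worked example: 1 + 3 + 10 + 30 + 100 + 90 = 234 mg.

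All three reproduce, so the two cut-offs mean full dosing through 1,000 mg and through 2,000 mg.

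**2. CRD of a child who ingests every dose and passes.**
- SAP 5.2.1, definition: 3,444 mg.
- SAP 5.2.1, calculation rule: the eCRF ED is blank, so CRD is missing.
- SAP 5.2.4: max(3,444, screening CRD). The screening steps stop at 300 mg and total 1 + 3 + 10 + 30 + 100 + 300 = 444 mg, so the maximum is 3,444 mg for any screening value.

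A child who reacts at the full 1,000 or 2,000 mg dose has a reported ED and is unaffected under every reading.

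**3. Does the 5.2.4 value reach the threshold endpoints?**
- It sits under Secondary analyses, with a lead-in limited to intercurrent events 1 and 3. In SAP Table 3, event 1 is early discontinuation with no challenge and event 3 is a challenge started but left incomplete. A pass is neither.
- The closing paragraph of 5.2.4, and 5.4.3, rule out imputation for other efficacy variables.
- SAP 5.4.3.1 points to the primary-analysis rules by event type. Those rules (5.2.4, Primary analysis) cite the modified baseline-carried-forward method (mBOCF) for ED only. They contain no CRD rule and do not cover a child with no intercurrent event.

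So the value exists in the SAP, but no sentence clearly takes it to these endpoints.

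**4. What a literal reading could do.** The documents give no pass rate, so every rate here is an assumption. Suppose passers make up the same share p, in both arms, of the children who truly reach 3,444 mg, and are scored as not reaching it. Then reported difference = true difference × (1 − p).

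| Assumed true rates, active vs placebo | True difference | p = 50% | p = 75% | p = 90% |
|---|---|---|---|---|
| 15% vs 3% | 12 points | 6 | 3 | 1.2 |
| 25% vs 5% | 20 points | 10 | 5 | 2 |

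The alternative is that passers are dropped from the denominator. Assume that in the active arm 10% react at the full 2,000 mg dose and 10% to 40% pass. The percentage reaching 3,444 mg is then 20% to 50% under 5.2.4. It is 10% if passers are scored as not reaching, and 10/90 = 11% to 10/60 = 17% if they are dropped. With 40% passing, both literal figures lie below the pass rate.

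**The case against.** The best defence is that the SAP works in two steps: 5.2.1 derives CRD from the eCRF, and 5.2.4 fills the gaps. The 5.2.4 sub-bullet names passers, and that clause would have no purpose if they fell outside it. SAP 5.4.3.1 is the endpoint-specific text and should prevail over the general no-imputation sentences. It leads to the primary rules, which themselves refer to the mBOCF text under Secondary analyses, where the CRD counterpart gives 3,444 mg. Much of this stands. It is the coherent reading and probably the intended one. But it takes two inferences that the SAP does not state, and the 5.2.1 rule still conflicts with it.

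The stakes are also low. SAP 5.4.3 makes these endpoints descriptive, and they are outside the hierarchy in SAP Table 1. The primary endpoint uses ED, which 5.2.1 repairs. A percentage reaching 3,444 mg below the percentage who passed should be noticed in quality control.

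A reader might infer three stronger things that the documents do not support:
- That the endpoints certainly lose the best responders. SAP 5.2.4 supplies a value for these children, and 5.4.3.1 can be read as reaching it.
- That the protocol's missing=failure rule would score a passer as a failure. The protocol endpoint is cumulative dose, and protocol 6.2.1.3.6 has the doses given and the peanut cumulative dose recorded in the e-CRF, so a passer's value is not missing under the protocol.
- That the SAP's change of name to cumulative reactive dose excludes children who did not react. SAP 5.2.1 defines CRD by doses taken, so nothing turns on the name.

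**Conclusion.** The inconsistency is real: SAP 5.2.1 yields a missing CRD where its own definition and SAP 5.2.4 yield 3,444 mg. The hierarchically tested secondary CRD analysis is covered by 5.2.4. For the two descriptive threshold endpoints the SAP can be read either way.

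A loss of passers is conditional on the 5.2.1 rule being programmed literally. The SAP appendices are redacted, so the programmed derivation cannot be checked. The size of any error cannot be determined from the documents, and the figures in the working rest on assumed rates. Its direction would be to understate the benefit if more children pass on active treatment. Severity is minor: wording to correct before programming.

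**What to change.** - **SAP 5.2.1:** state that if the 2,000 mg dose was taken without stopping symptoms, CRD is the sum of all doses given (3,444 mg if all were fully ingested) and is treated as observed. CRD is then missing only when the derived ED is missing.
- **SAP 5.2.4 and 5.4.3:** exempt the 5.4.3.1 endpoints from the no-imputation sentences, so that 5.4.3.1 alone governs them.
- **SAP 5.11:** list the change from the missing=failure rule of protocol 8.5.4. The present list mentions intercurrent-event handling only for the primary and secondary analyses.

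The cost is a few lines of SAP text and one line in the dataset derivation. No new data are needed, and the primary and secondary analyses do not change.

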### 5.2.2 Multiple Comparisons/Multiplicity

To handle multiple comparisons versus placebo, the overall type-I error will be controlled at a level of 5% (2-sided) by the use of a hierarchical inferential approach. The primary analysis in the FAS must be positive according to the success criterion (pre-specified threshold described in section 5.4.1). The first secondary efficacy analysis (difference in cumulative reactive dose) must meet its success criterion before drawing an inferential conclusion about the next secondary comparison (difference in peanut protein ED).

**Table 1 - Pre-defined hierarchical Order for Analysis of Efficacy Endpoints**

Order	Efficacy endpoints (at Month 12)	Population	Success criterion
1	Percentages of treatment responders	FAS	95% CI lower bound $\geq 15\%$
2	Peanut protein Cumulative Reactive Dose at Month 12	FAS	$p \leq 0.05$
3	Peanut protein Eliciting Dose at Month 12	FAS	$p \leq 0.05$

### 5.2.3 Stratification

An Interactive Web Response System (IWRS) randomized subjects and assigned the appropriate treatment number or kit number.

In the part B, the randomization scheme was on a 2:1 ratio to DBV712 at the selected dose (250  $\mu\text{g}$ ).

Randomization was stratified by center and managed centrally. The randomization scheme ensured that the ratio of active treatments to placebo was maintained.

However, due to the large number of centers, the analyses will not be stratified by center.

### 5.2.4 Handling of Missing Data

#### Primary analysis

Analyses of the primary efficacy endpoint will be based on the FAS. Depending on the type of intercurrent events, missing data will be imputed using:

- missing=failure imputation method for intercurrent event 1 (see section 5.4). Those subjects with missing peanut eliciting dose value at Month 12 will be considered as non-responders.
- multiple imputation for subjects with intercurrent events 2 and 5 (see section 5.4), who were unable to perform the DBPCFC (procedure cannot be performed due to Covid-19, child refused to

	Statistical Analysis Plan	
	EPITOPÉ (V712-304) – Statistical Analysis Plan	
	Référence du Document /Document Reference : CCI	Page : 21 / 74

CCI

ingest the formula due to fear, aversion...). For those subjects, the probability distribution that imputes the missing response will rely on placebo subjects with an available response and so the missing data would mimic placebo response. Imputations will be performed using SAS® MI procedure generating 100 sets of imputed data. Seed used for imputation will be specified (details on the implementation of multiple imputations are given in Appendix 8.2)

- modified Baseline Observation Carried Forward (mBOCF) method imputation for subjects with intercurrent event 3 (see section 5.4), who starting the DBPCFC at Month 12 and refusing to ingest the formula left due to fear, aversion, without any of the objective symptoms leading to ending the DBPCFC (stopping rules). This method will rely on mBOCF for ED detailed in next section “Secondary analyses”.

Sensitivity analyses will be performed on different sets and using other imputation methods for missing data (see section 5.4).

### Secondary analyses

Analyses of ED and CRD as continuous endpoints will be based on the FAS using:

- multiple imputation for subjects who were unable to perform the DBPCFC (intercurrent events 2 and 5, see section 5.4). For those subjects, the probability distribution that imputes the missing ED/CRD will rely on placebo subjects with an available response and so the missing data would mimic placebo response. Imputations will be performed using SAS® MI procedure generating 100 sets of imputed data. Seed used for imputation will be specified (details on the implementation of multiple imputations are given in Appendix 8.2)
- mBOCF method to impute missing data at Month 12 for subjects with intercurrent events 1 and 3 (see section 5.4):
  - mBOCF for ED is defined as follow:
    - If the DBPCFC is stopped without symptoms leading to ending the DBPCFC (stopping rules) or if the subject took the 2,000mg dose without any objective symptom leading to ending the DBPCFC, the ED value at Month 12 is considered as the maximum between:
      - the last dose given at Month 12 DBPCFC (if the last dose given at Month 12 DBPCFC is only partially ingested by the subject, then the rules as defined under partially ingested dose in section 5.4.1 will apply) AND
      - the ED value at screening
    - For the subjects who did not undergo the Month 12 DBPCFC, ED value at screening is carried forward at Month 12 using BOCF method.
  - mBOCF for CRD is defined as follows:
    - If the DBPCFC is stopped without symptoms leading to ending the DBPCFC (stopping rules) or if the subject took the 2,000mg dose without any objective symptom leading to ending the DBPCFC, the CRD value at Month 12 is considered as the maximum between:
      - the sum of all doses given at Month 12, including also the partial doses AND

CONFIDENTIEL / Ne pas diffuser sans autorisation de DBV

CONFIDENTIAL / Do not distribute without DBV authorization

	Statistical Analysis Plan	
	EPITOPÉ (V712-304) – Statistical Analysis Plan	
	Référence du Document /Document Reference : CCI	Page : 22 / 74

CCI

- the CRD value at screening
  - For the subjects who did not undergo the Month 12 DBPCFC, CRD at screening is carried forward at Month 12 using BOCF method.

No imputation will be performed for other efficacy, safety and exploratory parameters. In those instances, observed data will be used, excepted for laboratory results reported as below the lower detection limit (or reported above a specific value) which will be imputed as described in Section 5.1 and safety data where partial or missing data will be imputed according to the most conservative approach. (See section 5.5.1.2).

#### Dates of birth

- If only the day is missing, it will be imputed using the first day of the documented month.
- If the day and the month are missing, it will be imputed using the first of January of the documented year.

For analyses based on the actual age at baseline, the documented age in the IWRS will be used. Imputed date of birth will only be used for analyses based on age during the study, where the calculation using date of birth would be needed (e.g. date of 4th anniversary).

#### Dates of events

- Imputation rules of Treatment dates are defined in the section 5.2.6.1
- Imputation rules of AEs dates are defined in the section 5.5.1.2
- Imputation rules of Concomitant Medications dates are defined in the section 5.3.7

